10.4.2 Analysis of the Primary Efficacy Endpoint(s)

For all analyses, the standard assumptions of Gaussian residuals and quality of variance will be tested. If the standard assumptions are not met, a transformation will be performed (i.e. logarithm transformation). Results will be brought back to the original units and reported as geometric means with their corresponding lower and upper confidence limits.

For the assessment of number of days on supplemental oxygen therapy (i.e. count data), a Poisson, Negative Binomial (NB), Zero-Inflated Poisson (ZIP), or Zero-Inflated Negative Binomial (ZINB) model will be used.

A result will be considered statistically significant at the $p < 0.05$ level of significance. All analyses will be performed using SAS version 9.4 (SAS Institute Inc., Cary, NC).

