SAE	Serious Adverse Event/Serious Adverse Experience
SOP	Standard Operating Procedure
US	United States

Protocol Summary

Title	Efficacy of combined nebulized hypertonic saline and chest percussion therapy in acute viral bronchiolitis
Short Title	Combined nebulized hypertonic saline and chest percussion in pediatric bronchiolitis
Brief Summary	This study will examine the efficacy of combined nebulized hypertonic saline with chest percussion therapy in patients age 0 to 24 months admitted to the general inpatient pediatrics unit with acute bronchiolitis. 3% nebulized hypertonic saline treatments combined with 3 minutes of chest percussion therapy will be administered every 6 hours of patients selected for the study.
Phase	N/A
Objectives	Primary outcomes measured will be length of hospital stay and time on supplemental oxygen support, both to be measured in hours. The hypothesis will be that combined nebulized hypertonic saline and chest percussion therapy will decrease length of hospital stay and time on supplemental oxygen support. Secondary outcomes measured will be clinical response (respiratory rate, heart rate, pulse oximetry reading), subjective perceptions of caregivers and health care team, and cost-benefit.
Methodology	Cross-sectional quasi-experimental, open, non-randomized clinical study
Endpoint	Primary endpoints include length of hospital stay and time on supplemental oxygen therapy. Secondary endpoints include trend of respiratory rate, heart rate, and pulse oximetry reading following treatments and subjective perceptions of patients' clinical status based on caregiver and health care team.
Study Duration	12 months
Participant Duration	The duration of participation will begin from time of admission to the general inpatient pediatrics unit until time of discharge from the general inpatient pediatrics unit. This duration may vary from patient to patient, on average will last approximately 1-5 days.
Duration of IP administration	The duration of product administration will begin from time of admission to the general inpatient pediatrics unit until time of discontinuation of supplemental oxygen therapy. This duration may vary from patient to patient, on average will last approximately 1-5 days.
Population	Pediatric patients age 0 to 24 months admitted to the general pediatrics unit admitted for acute bronchiolitis requiring supplemental oxygen therapy
Study Sites	NYU Langone Hospital – Long Island, general inpatient pediatrics unit (NP5)

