4.2 Study Endpoints**4.2.1 Primary Study Endpoints**

The primary study endpoints will be length of hospital stay expressed in days and the time on supplemental oxygen support expressed in days, and these endpoints will be compared between the control and experimental group.

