4.2.3 Exploratory Endpoints

There are no exploratory endpoints in this study.

5 Study Enrollment and Withdrawal**5.1 Inclusion Criteria**

In order to be eligible to participate in this study (experimental arm), an individual must meet all of the following criteria:

1. Age 0 to 24 months
2. Admitted to the general inpatient pediatrics unit
3. Has a diagnosis of acute bronchiolitis
4. Receiving supplemental oxygen support

Data collected for the control arm will be obtained via retrospective chart review for patients meeting the following inclusion criteria:

1. Age 0 to 24 months
2. Admitted to the general inpatient pediatrics unit

3. Has a diagnosis of acute bronchiolitis
4. Receiving supplemental oxygen support

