7.3.4 Final Study Visit

Final Study Visit (Day of hospital discharge)

- Record adverse events as reported by participant or observed by investigator.
- Record vital signs to include respiratory rate, heart rate, and oxygen saturation.
- Record time of supplemental oxygen support order discontinuation.
- Record subjective responses from providers and caretakers on participants' clinical response to treatment.
- Record participant's adherence to treatment regimen.

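### Time on supplemental oxygen is an elapsed duration, but 10.4.2 calls it count data and requires one of four count models with no rule for choosing

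*Combined protocol and SAP*

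**What the plan says.** The Protocol Summary (Objectives) sets the unit for both primaries: "Primary outcomes measured will be length of hospital stay and time on supplemental oxygen support, both to be measured in hours". Section 4.2.1 instead has "the time on supplemental oxygen support expressed in days", and the hypotheses in 10.2 also speak of a number of days. No section says how an elapsed time becomes a whole number of days.

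Section 10.4.2 gives the analysis: "For the assessment of number of days on supplemental oxygen therapy (i.e. count data), a Poisson, Negative Binomial (NB), Zero-Inflated Poisson (ZIP". ZINB is the fourth and last option, and use of one of the four is mandatory. The same sentence stands in the Protocol Summary, 4.1, 10.4.3 and 10.4.7.2. No criterion for choosing among the four models is given, and no correction for over- or under-dispersion.

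Entry criterion 4 in section 5.1, for both arms, is "Receiving supplemental oxygen support". The Protocol Summary describes the population as "admitted for acute bronchiolitis requiring supplemental oxygen therapy". At the final visit (7.3.4) staff are to "Record time of supplemental oxygen support order discontinuation". No section expressly calls for an oxygen start time.

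Section 1 says that data collection will begin before a biostatistician is identified, and that analysis will wait for that appointment.

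**The concern.** A count model is for numbers of events. A Poisson model ties the variance to the mean, and for a duration that tie has no basis: rescaling time multiplies the mean by 24 and the variance by 24² = 576, so the equality cannot hold in both hours and days. The plan names both units.

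Zero-inflated models add a class of patients whose outcome is zero by nature. Here every eligible child has a positive duration.

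At stake is the p-value and confidence interval of a primary endpoint. The study is unblinded, its controls are historical, and the outcome data will exist before anyone is in post to choose the model. Four candidates without a rule, on an endpoint with two stated units, leave the primary result open to choices made after the data are in hand.

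**Working it through.** **The plan's own figure.** Section 10.5 gives 228 subjects (114 per group) from mean 6.5 days, SD 3.5 days, a 20% decrease (1.3 days), alpha 0.05 and power 0.80. Two-sided, n = 2 × (1.960 + 0.842)² × 3.5² / 1.3² = 113.8, so 114 per group. It reproduces, but it covers length of stay only. No mean, SD or power is given for oxygen time, so the means and coefficients of variation (CV) below are assumptions. CV 0.54 is 3.5/6.5, borrowed from length of stay.

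**Unit dependence (algebra).** The Poisson Wald statistic is z = log(S0/S1) / sqrt(1/S0 + 1/S1), where S0 and S1 are the group totals. Going from days to hours leaves the numerator unchanged and divides the standard error by sqrt(24) = 4.90.

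Example with 114 per group, control mean 3 days and an observed 5% difference (2.85 days), so that S0 = 342 and S1 = 324.9:
- Days: SE = 0.0775, z = 0.0513/0.0775 = 0.66, p = 0.51.
- Hours: SE = 0.0158, z = 3.24, p = 0.0012.

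**Calibration.** With φ = variance/mean, Poisson type I error at nominal 0.05 is about 2 × [1 − Φ(1.96/√φ)]. For mean 6.5 and SD 3.5 days, φ = 12.25/6.5 = 1.88, giving 15%. In hours φ = 84²/156 = 45.2, giving 77%.

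Simulated type I error under no difference (gamma durations, 114 per group, 20,000 runs):

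| Mean (days), CV | Days rounded up | Nearest | Rounded down | Hours |
|---|---|---|---|---|
| 6.5, 0.54 | 13.4% | 14.8% | 16.5% | 76.5% |
| 3, 0.54 | 2.5% | 3.8% | 5.9% | 66.9% |
| 2, 0.54 | 0.6% | 1.2% | 3.1% | 60.4% |
| 3, 0.8 | 12.6% | 16.1% | 19.5% | 77.2% |
| 2, 0.8 | 5.7% | 9.2% | 13.8% | 72.4% |

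Allowing for simulation error, the ranges are about 0.5% to 20% in whole days and 59% to 78% in hours. A t-test on log duration stays at about 5% in all five settings. The ranges cover these five combinations only. Mean 6.5 with CV 0.8 would lie higher: φ = 0.64 × 6.5 = 4.16, about 34% in unrounded days.

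**Negative binomial.** In one simulated data set (mean about 3 days, CV 0.54), NB gave p = 0.102 in whole days and 0.097 in hours, while Poisson gave 0.102 and 8 × 10⁻¹³. In 400 null data sets NB in hours rejected 6.5% (Monte Carlo SE about 1.1 points). In whole days the NB fit returned no p-value in 159 of the 400. NB can absorb excess variance but not a variance below the mean, and with CV 0.54 and mean 3 days φ is 0.29 × 3 = 0.87.

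**Zeros.** There are none in exact time or in days rounded up. Rounding to nearest turns stays under 12 hours into zeros (0.1% to 13% of patients over the five settings). Rounding down does so for stays under 24 hours (0.7% to 31%).

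**The case against.** The best defence has four parts, and each limits the point.

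1. Every count-model sentence says days; hours appear only in the synopsis objectives. A reader might infer that the plan prescribes Poisson regression on hours, with a type I error near 77%. It does not. The hours column shows what would follow if the synopsis unit were taken up.
2. NB is on the list, and its estimated dispersion absorbs most of the change of unit; by the same logic so does that of ZINB, which was not fitted. A statistician who checked dispersion could choose well from within the list. This stands, so unit dependence is a fault of Poisson and ZIP, not of all four models. But the plan has no rule that leads to NB.
3. The 6.5-day mean belongs to length of stay, and the synopsis puts treatment until oxygen stops at about 1 to 5 days on average. Within that range at CV 0.54, Poisson error in whole days is about 0.6% to 6% at means of 2 to 3 days and 9% to 13% at 5 days. So the error in days may be modest or even conservative; its direction cannot be known beforehand.
4. A reader might infer that no zero can appear in the data. True durations exceed zero, but the rounding convention is unstated, so zeros can be recorded. They would be rounding artefacts, not the structural zeros that ZIP and ZINB assume.

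Nor do the documents support a claim of a large power gain. For a 20% reduction at mean 3 days and CV 0.54, a log-scale test has about 91% power only if durations are lognormal. With gamma durations it is about 83%, against 76% to 86% for Poisson in days depending on rounding.

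**Conclusion.** The point holds. The unit conflict, the count label on a duration, the absent selection rule and the lack of structural zeros can all be read directly from the documents. The factor of 4.9 in z for Poisson and ZIP is algebra and needs no assumption about the data. The type I error ranges rest on assumed gamma durations, means and CVs, and they illustrate the scale rather than predict it.

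This is more than missing detail: 10.4.2 states a rule for a primary endpoint, and some ways of following it give a test that is not valid. The general t-test, Mann-Whitney and log-transform wording in 10.4.1 and 10.4.2 does not displace that specific instruction. It should be settled before outcome data are examined.

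**What to change.** - State one unit, hours, in the Protocol Summary, 4.2.1, 10.2 and 10.4.2.
- Define oxygen time from a stated start (for example unit admission, or first charted oxygen on the unit) to charted discontinuation, the same way in both arms.
- Delete the Poisson/NB/ZIP/ZINB sentence in the Protocol Summary, 4.1, 10.4.2, 10.4.3 and 10.4.7.2.
- Analyse the duration as continuous, using the log transformation that 10.4.2 already allows, and report a geometric-mean ratio with 95% CI. A time-to-cessation model is optional as a sensitivity analysis.

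The plan changes are wording only: no added patients or visits. The cost is in data abstraction. Start and stop times must be taken from the charts of both arms, the documents do not expressly provide for a start time, and charting for the historical controls may be less precise.

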10.4.3 Analysis of the Secondary Endpoint(s)

For all analyses, the standard assumptions of Gaussian residuals and quality of variance will be tested. If the standard assumptions are not met, a transformation will be performed (i.e. logarithm transformation). Results will be brought back to the original units and reported as geometric means with their corresponding lower and upper confidence limits.

For the assessment of number of days on supplemental oxygen therapy (i.e. count data), a Poisson, Negative Binomial (NB), Zero-Inflated Poisson (ZIP), or Zero-Inflated Negative Binomial (ZINB) model will be used.

A result will be considered statistically significant at the $p < 0.05$ level of significance. All analyses will be performed using SAS version 9.4 (SAS Institute Inc., Cary, NC).

10.4.4 Safety Analyses

Adverse events will be coded via Medical Dictionary for Regulatory Activities (MedDRA) and each adverse event will be counted once for occurrence. The severity, frequency and relationship of the adverse event to the study agent will be presented by the System Organ Class (SOC) and preferred term groupings. Information that will be reported about each adverse event will include start date and time of study agent, stop date and time of study agent, severity, relationship to event to study agent, and outcome. Adverse events will be ascertained and reported by the primary investigator. Adverse events leading to premature discontinuation from the study and serious adverse events requiring emergent treatment will be presented in a summarized listing.

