2.2.1 Clinical Data to Date

Hypertonic saline nebulization

Hypertonic saline nebulization is one of the adjuvant therapies that has been used for management of acute viral bronchiolitis. Theories behind its efficacy lie within the proposed effects of airway hydration and reduction of edema as well as mucus clearance. [1] A 2017 Cochrane systematic review showed that patients with acute bronchiolitis who received hypertonic saline nebulization treatments had a significantly shorter length of stay in comparison with patients who received normal saline nebulization treatments. This shows that there may be some benefit in using hypertonic saline nebulization in the management of acute bronchiolitis. The review however did show a low quality in evidence as well as large variations between studies. [5] The 2014 American Academy of Pediatrics clinical practice guidelines has a moderate recommendation against the use of hypertonic saline nebulization in treatment for acute bronchiolitis, with the notion that new information may arise as further evidence on this treatment option emerges. [4] Because of the limited evidence and low quality of studies, the need for standardized and multi-centered studies remains in regards to the use of hypertonic saline nebulization in acute bronchiolitis.

The side effect profile of hypertonic saline nebulization treatments remains low. There is some concern with treatments causing bronchospasm, but a retrospective cohort studied showed a 0.3% rate of occurrence of this side effect. The concern for bronchospasm seems to increase with the increase in concentration of hypertonic saline nebulization treatments, as formulations range from 3% to 7%. Other adverse events were reported in this study and showed a 1.0% rate of occurrence, and these events involved excessive coughing, which was transient. [6] Other side effects that have been reported such as hypernatremia, desaturation, bradycardia, vomiting and diarrhea were minor and spontaneously resolved. [5]

Given the evidence of potential benefits of nebulized hypertonic saline in improvement of airway hydration, edema and clearance in conjunction with a very low side effect profile, its use in a study to determine its efficacy is justifiable.

Chest percussion therapy

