2.4 Potential Risks & Benefits

2.4.1 Known Potential Risks

The side effect profile of hypertonic saline nebulization treatments remains low. There is some concern with treatments causing bronchospasm, but a retrospective cohort studied showed a 0.3% rate of occurrence of this side effect. The concern for bronchospasm seems to increase with the increase in concentration of hypertonic saline nebulization treatments, as formulations range from 3% to 7%. Other adverse events were reported in this study and showed a 1.0% rate of occurrence, and these events involved excessive coughing, which was transient. [6] Other side effects that have been reported such as hypernatremia, desaturation, bradycardia, vomiting and diarrhea were minor and spontaneously resolved. [5] There are no long-term risks associated with nebulized hypertonic saline and it is considered safe and inexpensive.

The side effect profile of chest percussion therapy, adverse effects of concern include excessive coughing and irritability. There were two case reports of rib fractures in children who received chest physiotherapy; however these were related to the more invasive forced expiratory techniques. Overall, the evidence lacked any statistically significant adverse outcomes following use of chest percussion therapy in children. [7] It can be concluded that chest percussion therapy is the least invasive of the chest physiotherapy techniques and the potential adverse effects of chest percussion therapy remain low.

There are no foreseeable physical, psychological, social, legal, or economic risks to participants by virtue of participation in this study. The value of information to be gained from this study may further guide clinicians on a more evidence-based approach to treatment of acute bronchiolitis in pediatric patients.

Because the study involves pediatrics, it is considered a study on a vulnerable population. There are no additional risks than those described previously.

Minimizing Risks

Because the study involves pediatrics, it is considered a study on a vulnerable population. There are no additional risks than those described previously.

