8.1.3 Definition of Unanticipated Problems (UP)

Unanticipated Problems Involving Risk to Subjects or Others

Any incident, experience, or outcome that meets all of the following criteria:

- Unexpected in nature, severity, or frequency (i.e. not described in study-related documents such as the IRB-approved protocol or consent form, the investigators brochure, etc)
- Related or possibly related to participation in the research (i.e. possibly related means there is a reasonable possibility that the incident experience, or outcome may have been caused by the procedures involved in the research)
- Suggests that the research places subjects or others at greater risk of harm (including physical, psychological, economic, or social harm).

This definition could include an unanticipated adverse device effect, any serious adverse effect on health or safety or any life-threatening problem or death caused by, or associated with, a device, if that effect, problem, or death was not previously identified in nature, severity, or degree of incidence in the investigational plan or application (including a supplementary plan or application), or any other unanticipated serious problem associated with a device that relates to the rights, safety, or welfare of subjects (21 CFR 812.3(s)).

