8.2.3 Expectedness

[name], the primary investigator, will be responsible for determining whether an AE is expected or unexpected. An AE will be considered unexpected if the nature, severity, or frequency of the event is not consistent with the risk information previously described for the study agent.

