8.3 Time Period and Frequency for Event Assessment and Follow-Up

The occurrence of an AE or SAE may come to the attention of study personnel during study visits and interviews of a study participant presenting for medical care, or upon review by a study monitor. All AEs including local and systemic reactions not meeting the criteria for SAEs will be captured on the appropriate RF. Information to be collected includes event description, time of onset, clinician's assessment of severity, relationship to study product (assessed only by those with the training and authority to make a diagnosis), and time of resolution/stabilization of the event. All AEs occurring while on study must be documented appropriately regardless of relationship. All AEs will be followed to adequate resolution.

Any medical condition that is present at the time that the participant is screened will be considered as baseline and not reported as an AE. However, if the study participant's condition deteriorates at any time during the study, it will be recorded as an AE. UPs will be recorded in the data collection system throughout the study.

Changes in the severity of an AE will be documented to allow an assessment of the duration of the event at each level of severity to be performed. AEs characterized as intermittent require documentation of onset and duration of each episode.

The PI will record all reportable events with start dates occurring any time after informed consent is obtained until 7 (for non-serious AEs) or 30 days (for SAEs) after the last day of study participation. At each study visit, the investigator will inquire about the occurrence of AE/SAEs since the last visit. Events will be followed for outcome information until resolution or stabilization.

All unresolved adverse events should be followed by the investigator until the events are resolved, the subject is lost to follow-up, or the adverse event is otherwise explained. At the last scheduled visit, the investigator should instruct each subject to report any subsequent event(s) that the subject, or the subject's personal physician, believes might reasonably be related to participation in this study. The investigator should notify the study sponsor of any death or adverse event occurring at any time after a subject has discontinued or terminated study participation that may reasonably be related to this study.

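### The safety analysis counts adverse events by occurrence, with no count of children affected and no safety denominator, so it cannot give the proportion of infants harmed

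*Combined protocol and SAP*

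**What the plan says.** Section 10.4.4 is the whole safety analysis. Events are coded in MedDRA, and "each adverse event will be counted once for occurrence". Severity, frequency and relationship are then presented by system organ class and preferred term. The section does not say whether frequency is over children, treatments or days, and it defines no safety population.

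Section 8.3 adds that "AEs characterized as intermittent require documentation of onset and duration of each episode". Section 7.3.3 has adverse events recorded once per shift.

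Frequency also enters two judgements. Section 8.2.3: "An AE will be considered unexpected if the nature, severity, or frequency of the event is not consistent with the risk information previously described". Section 8.1.3 lists "Unexpected in nature, severity, or frequency" as one of three conditions for an unanticipated problem, all of which must be met.

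The risk information gives two rates. For bronchospasm, Section 2.4.1 says "a retrospective cohort studied showed a 0.3% rate of occurrence of this side effect". For excessive coughing, Section 2.2.1 says "Other adverse events were reported in this study and showed a 1.0% rate of occurrence". Neither rate is stated to be per treatment or per child.

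**The concern.** The first question asked of a safety table in infants is what proportion had the event. A count of occurrences does not answer it when each child is exposed many times, because it mixes the number of children affected with the number of recurrences per child. Cough and bronchospasm, the events the protocol itself names, can plausibly recur from one treatment to the next.

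Two further problems follow. Treatment continues only while the child is on oxygen, so the opportunity for events grows with time on oxygen, a primary endpoint under Section 4.2.1; a raw count therefore mixes risk with duration. And the only benchmarks in the protocol are percentages without a unit, so a count without a denominator cannot be placed against them. Section 8.7 relies on the investigator's periodic review of aggregate adverse events with no predefined stopping rules, so a readable summary matters.

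**Working it through.** **Inputs**
- Treated children: 114 (Section 10.5).
- Frequency: every 6 hours, so 24/6 = 4 per day (Sections 6.1.5 and 6.1.11).
- Duration: about 1 to 5 days (Protocol Summary, duration of IP administration). The 3-day midpoint and full adherence are assumptions.
- Background rates: 0.3% and 1.0% (Sections 2.2.1 and 2.4.1), unit not stated.
- The figure of 14 events is chosen for illustration; it is not in the documents.

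**The plan's own number.** The 114 reproduces from Section 10.5. With SD 3.5 days, a difference of 0.20 × 6.5 = 1.3 days, two-sided alpha 0.05 and power 0.80, n per group = 2 × (1.96 + 0.8416)² × 3.5² / 1.3² = 113.8, rounded up to 114, or 228 in total. Nothing below changes it.

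**Same events, two denominators.** Treatments = 114 × 4 × days. Fourteen events give:

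| Days | Treatments per child | All treatments | Events per 100 treatments | Events per 100 children | Ratio |
|---|---|---|---|---|---|
| 1 | 4 | 456 | 3.07 | 12.3 | 4 |
| 3 | 12 | 1,368 | 1.02 | 12.3 | 12 |
| 5 | 20 | 2,280 | 0.61 | 12.3 | 20 |

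The ratio is simply the number of treatments per child.

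**Same events, different numbers of children.** Fourteen events could come from:

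| Children affected | Percent of 114 |
|---|---|
| 14 | 12.3 |
| 7 | 6.1 |
| 4 | 3.5 |
| 2 | 1.8 |
| 1 | 0.9 |

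The last row needs one child to have more events than treatments at 12 treatments per child. If at most one event is logged per treatment, the floor is two children, 1.8%. A table of 14 occurrences looks the same in every row.

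**Against the background rates, at 3 days**
- 1.0% per treatment: 0.01 × 1,368 = 13.7 events expected. Per child: 0.01 × 114 = 1.14 children expected.
- 0.3% per treatment: 0.003 × 1,368 = 4.1 events expected. Per child: 0.003 × 114 = 0.34 children expected.

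**The number of children is open too.** Sections 5.6 and 10.6 speak of about 200 enrolled to obtain 114 evaluable, and Section 10.4.5 removes children who leave early, including for adverse events. Fourteen affected children would be 14/114 = 12.3% or 14/200 = 7.0%.

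**The case against.** The strongest reply is that Section 8.3 treats the adverse event as the unit and episodes as detail recorded within it. On that reading, a child who coughs after 12 treatments has one intermittent event with 12 documented episodes, counted once. This is a fair reading, and the wording of Section 10.4.4 does not exclude it. The inflation therefore depends on recurrences being logged as separate events, which the plan leaves unsettled. On either reading, no count of children and no denominator are specified.

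Second, Section 10.4.1 promises frequencies and percentages for categorical variables by group, and a percentage implies a denominator. But that text is general, does not mention adverse events, and does not settle which children make up N.

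Third, if records are kept by child, a per-child table can be derived later without loss. That is true, and it is why the change is cheap; it does not say which table will be reported.

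Fourth, a reader might infer that the counting rule could reverse a decision on whether an event is unexpected. The documents do not support this. Section 8.2.3 leaves the judgement to the investigator, with no numeric threshold; nature or severity alone can suffice; Section 8.1.3 also requires relatedness and greater risk of harm; and nothing links the Section 10.4.4 table to either judgement. What stands is that the frequency part of the judgement could be harder to make.

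Fifth, a reader might add that intervals around the counts would be too narrow because repeat events in a child are correlated. No interval or test on adverse event counts is planned, so there is nothing for that criticism to attach to.

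**Conclusion.** The point holds as a weakness in the planned safety summary. As written, Section 10.4.4 cannot give the proportion of infants harmed, and its output cannot be compared cleanly with the 0.3% and 1.0% rates.

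The size depends on exposure and clustering. Over 1 to 5 days, the ratio of per-child to per-treatment rates is 4 to 20. At an assumed 3 days with full adherence and 114 children, 14 events are 1.0% of treatments and 0.9% to 12.3% of children. It would be wrong to read 1% versus 12% as study figures: the 12% needs 14 different children, and both need the 3-day assumption. Which unit the background rates carry cannot be settled from the documents.

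The sample size and the efficacy analyses are unaffected.

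**What to change.** In Section 10.4.4:
- Count each child once per preferred term, at worst severity, and report n/N (%) with an exact 95% interval.
- Define N as all children who received at least one study treatment, including those withdrawn early or because of adverse events. State that the early-withdrawal rule in Section 10.4.5 does not apply to safety, and align Section 5.7.2, which both bars use of withdrawn participants' information and asks for safety follow-up.
- State whether recurrences are logged as one intermittent event or as separate events. Report the number of events, and events per 100 nebulized doses.

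In Sections 2.2.1 and 2.4.1, state the unit of the 0.3% and 1.0% rates, and make any comparison under Section 8.2.3 on that same unit.

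The cost is one extra table column and a slightly longer safety section. Nebulized doses are already tracked in the medication administration record (Section 6.1.10). No equivalent tracking is stated for percussion, so the exposure rate should be per nebulized dose unless percussion sessions are also recorded.
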